
Date: _____

HOVER PROTOCOL SUMMARY

Title:	The HOVER Study: Heterotopic Implantation Of the Sapien 3 Transcatheter Aortic Valve in the Inferior Vena cava for the treatment of severe tricuspid Regurgitation
Design:	This is a prospective multi-center, non-blinded (open label), non-randomized safety and feasibility study of the heterotopic implantation of the Sapien 3 valve in the inferior vena cava for the treatment of severe tricuspid regurgitation in patients who are inoperable or at a very high surgical risk for tricuspid valve replacement. A total of 15 patients will undergo implantation. Primary endpoints will be assessed at 30-days and 6-months. This study is an off-label use of an FDA-approved and commercially available medical device.
Study Objectives:	#1: Determine the short term safety (<30 days) of Caval Valve Implant (CAVI) #2: Determine the intermediate term (6 months) efficacy of CAVI on palliation of patient symptoms of right heart congestion.
Primary Endpoints:	#1: Safety as defined by successful vascular access without unplanned major vascular complication as defined by VARC-2, delivery and retrieval of the transcatheter valve delivery system, correct position of both the vascular stent(s) and transcatheter valve in the IVC, a single valve placed within the IVC, and no need for additional surgery or re-intervention (including drainage of pericardial effusion) with the patient being alive at 30-days. #2: Efficacy as defined by Improvement of KCCQ score >15, or improvement in 6-minute walk test (6MWT)>70 meters or improvement of greater than 6% of peak Vo2 in cardiopulmonary exercise testing.
Population:	Patients with severe symptoms (NYHA class III-IV) and signs of peripheral and venous congestion (specifically lower extremity edema and abdominal ascites requiring diuretics), resulting from documented severe tricuspid regurgitation. These patients may benefit from tricuspid valve repair or replacement, but are believed to be at high risk or are deemed inoperable for standard tricuspid valve surgery as assessed by at least one cardiac surgeon.
Phase:	1-2
Clinical Sites:	
 1. Henry Ford Hospital, Detroit, Michigan – site PI: [name] [name] (Coordinating Center) 2. Temple University Hospital, Philadelphia, Pennsylvania – site PI: [name], DO 3. University of California San Francisco, San Francisco, California – site PI: [name] 4. Baptist Hospital of Miami, Miami, FL – site PI: [name]

1.0 BACKGROUND

Severe tricuspid regurgitation (TR) is an under treated disease state associated with significant morbidity and mortality. Nath and colleagues showed a 1-year mortality of 33.1% in patients diagnosed with severe tricuspid regurgitation¹. In the United States alone, 1,600,000 patients are diagnosed with severe tricuspid regurgitation each year, while only 8,000 (less than 1%) are treated with tricuspid valve surgery². The reasons for this are varied, however, many of these patients who are not treated go on to exhibit signs of central and peripheral venous congestion, including irreversible hepatic cirrhosis and chronic kidney disease. This creates a vicious spiral, in which those patients who are initially good operative candidates may become high risk or inoperable for conventional tricuspid valve surgery. Additional therapeutic options are therefore needed for these patients and their treating physicians.

Currently, there are no specifically designed devices for the transcatheter treatment of tricuspid valve disease. As a result, the treatment of these patients to date has relied on the off-label use of transcatheter aortic valve technology. Multiple case reports have shown the feasibility of percutaneous transcatheter aortic valve implantation within degenerated tricuspid valve bioprostheses or “valve-in-valve”^{3,4}. The experience is less robust for transcatheter tricuspid replacement within a native tricuspid valve⁵ and is likely limited in part to the annular dilatation which is present in patients with severe TR⁶. Despite this promising experience with transcatheter aortic valve placement directly within the tricuspid valve, long term data is lacking, and recent reports have demonstrated early valve failure in patients using this technique⁷.

Recently, caval valve implant of the Edwards Sapien Transcatheter valve for treatment of severe tricuspid regurgitation has shown promise as an additional therapy for patients with severe TR who are high risk or inoperable. Placement of a valve in the right atrial (RA)/caval junction would in theory prevent the massive reflux of blood into the IVC, thereby protecting the hepatic, renal, and lower extremity veins from volume overload. Santhanakrishnan and colleagues evaluated the effects of placing a unidirectional valve in the IVC in a bench model simulating a Fontan procedure, in which the SVC and IVC are directly anastomosed to the right and left pulmonary artery in those patients with one ventricle. Although short term effects of this procedure are favorable, long term patients go on to develop elevation in the systemic venous pressure from retrograde flow in expiration, particularly to the hepatic veins. In their study, the authors created a flexible wall model to simulate the IVC/SVC/PA connections. Using a Medtronic melody valve placed in the IVC in a sub-diaphragmatic position, they demonstrated a significant decrease in hepatic venous pressure through 20% of the cardiac cycle, with minimal gradient across the valve. They concluded this therapy may have potential for lowering hepatic venous pressure by arresting retrograde flow occurring in the IVC⁸.

The first in-vivo animal experience of this procedure was by Corno and colleagues in 2003⁹. In their study, bovine jugular xenografts were mounted on self-expanding nitinol stents and placed in the IVC of 5 adult pigs. Animals were anesthetized and the diameter and length of the IVC was measured using Intravascular ultrasound (IVUS). After placement of the valve, pressures were measured proximal and distal to assess for any gradients. IVUS showed partial opening and closing of the valve, with complete closure occurring during deep breaths. Autopsy showed adequate positioning of the valve stent without any deformation, with the proximal most portion of the valve 2cm proximal to the right atrial junction without any deformation of the valved stent. Sochmann et al performed twin valve caval stenting in a series of studies of three sheep and one swine. In their series, severe TR and reflux into the SVC and IVC was induced through papillary muscle avulsion in sheep, while the swine served as a control. Self-designed stents were placed in the caval veins through a 12-French sheath. 5-French pigtail catheters

were introduced into the femoral and jugular veins so that bicaval venography could be performed. In the swine, the valve functioned well for 3 hours without a position change and remained stable on necropsy. In 3 sheep, after placement of the stents, right ventricular (RV) angiography demonstrated retrograde filling of the SVC and IVC to the valves but not beyond¹⁰. At necropsy, the valve position remained stable.

Contemporary animal models have confirmed and expounded on these early results. Lauten and colleagues created acute severe TR in a sheep model via papillary muscle and chordae avulsion¹¹. Successful creation of TR was verified by a prominent ventricular (v) wave which was present in the central venous pressure tracing. Self-expanding nitinol stents containing a porcine pulmonary valve were placed in the superior vena cava (SVC) and inferior vena cava (IVC). In both an acute group (n=9) and chronic group (n=4), a significant decrease in the v-wave was demonstrated post-implant with an accompanying increase in cardiac output. At autopsy in the chronic group, the stents were covered with fibrous tissue and adhered strongly to the vessel wall. In one animal in the acute group, the SVC valve embolized into the right atrium with resultant hemodynamic instability. This did not cause immediate death. Autopsy showed correct device position in all successfully treated animals.

2.0 PROJECT PLAN

2.1 Rationale for Study

Severe TR is characterized by right heart congestion and volume overload¹⁵. Non-surgical treatment for TR relies on the administration of increasing doses of diuretic therapy to promote diuresis and volume contraction. However, many patients go on to become refractory to chronic diuretics over time. This is in part to the effects on chronic right heart congestion on the kidney. Based on previous studies, we believe that protection of the hepatic and renal veins with a one-way valve from the transmitted TR will allow for continued diuresis, and improvement in symptoms. Although CAVI has shown improvements in right heart congestion in a small series of patients, several questions remain. Previous studies have not clearly excluded TR that can occur with pulmonary arterial hypertension (PAH.) As 2/3 of the regurgitant flow from tricuspid regurgitation is directed to the IVC, the effects of redirection of this flow to the SVC are unknown. The degree of TR can be sensitive to changes in pre-load. It remains unclear if improvement in right heart congestion may therefore also affect degree of TR and indices of right ventricular (RV) function. Finally, the durability of the procedure beyond the intermediate term (6 months) is not well characterized. To help clarify these issues, we have created the Heterotopic Implantation Of the Edwards Sapien 3 Transcatheter Aortic Valve in the Inferior VEna cava for the treatment of severe Tricuspid Regurgitation study.

2.2 Design:

This is a prospective multi-center, non-blinded (open label), non-randomized safety and feasibility study of the heterotopic implantation of the Edwards Sapien 3 valve in the inferior vena cava for the treatment of severe tricuspid regurgitation in patients who are inoperable or at a very high surgical risk for tricuspid valve replacement. Patients enrolled will have severe TR and cardiac symptoms of right heart congestion in whom conventional tricuspid valve surgery (TVR) would be associated with high risk. Severe TR is defined by a vena contracta width > 7mm OR evidence of systolic hepatic vein flow reversal OR visible tricuspid valve coaptation defect + dense/triangular continuous wave with early peaking as assessed by continuous wave signal AND a very large central jet or eccentric wall impinging jet as assessed by color flow. ¹⁶. All patients must be on diuretics with documented evidence of continued venous congestion, such as lower extremity or abdominal wall edema.

All patients will be evaluated by at least one cardiac surgeon. The cardiac surgeon must agree that based on his assessment the patient is high risk or inoperable for TVR as per the surgical office note and attached (appendix E). Most inoperable patients have elevated STS risk scores including one or more STS risk elements that exceed thresholds considered safe for operation. A common example is respiratory disease, for which the STS risk-scoring threshold usually signals increased risk in operable patients, but which may be severe enough in a given patient to explain inoperability. In trials of TAVR, oxygen dependency in particular, has been independently associated with increased one-year mortality¹⁷. Other "inoperable" patients, regardless of STS score, are rendered inoperable by severe comorbidities of the low-prevalence, high-heterogeneity variety that are difficult to represent statistically and are not part of the STS risk model. Common examples include liver disease, porcelain aorta, chest wall abnormalities, and frailty. Chest wall abnormalities may include prior chest irradiation, a graft close to the sternum, or an absent or reconstructed sternum^{18,19}. It must be acknowledged that "inoperable" is frequently an integration of multiple dimensions of an individual patient in whom no simple, single-factor quantifiable line can be drawn between operable and "inoperable." Factors which make a patient high risk or inoperable will be clearly delineated in the patient's surgical evaluation. The "operable" patient will have characteristics which include a normal RVEF, normal creatinine, no previous open heart surgeries, preserved left ventricular ejection fraction. As the STS is undefined for these patients, should a patient have no other characteristics which make them high risk, an STS score for a simulated mitral valve procedure of <5 can also be considered in declaring a patient operable.

2.2.1 Definition of the Heart Team

When a potential subject is identified in the clinical practice of a participating site, the subject will be referred to the site heart team. The goal of the heart team is to optimize patient selection and improve procedural success. Originally intended for transcatheter aortic valve replacement (TAVR) decision making, the concept of the heart team has expanded to involve patients with structural or complex coronary artery disease in whom the participation of multiple physicians from differing areas of expertise is beneficial^{20 21}. Ideally, this team is comprised of an interventional cardiologist and cardiac surgeon at the core, with other expertise from advanced imaging, cardiac anesthesia, and heart failure as important adjuncts. Patients are seen individually by physicians, or, as part of a dedicated visit to multiple specialties in the form of a valve "clinic." After patients are evaluated, the members of the heart team will discuss the patient's case at a weekly conference. Here, a patient's clinical history and clinical data are reviewed, and a group recommendation is made. If after evaluation by an interventional cardiologist, heart failure specialist, and cardiac surgeon, as well as presentation at the local heart team conference, a patient is deemed a suitable candidate for the trial, they will be presented to the executive committee of the trial. The credentialing of heart team members will be the responsibility of the local heart team site.

2.2.2 Core Lab

Either concomitantly or after decision by the local heart site to presentation to the executive committee, baseline echocardiograms and CT scans will be reviewed by the coordinating center (Henry Ford Hospital) to confirm severe TR and anatomic suitability for implant.

2.2.3 The Executive Committee

The purpose of presentation of patients to the executive committee is to provide additional consultation from experts to further review and approve the selection prior to the patient being enrolled in the trial. The executive team will be comprised of the site PI from each site. The presentation will occur in the form of a conference call which is open to any member of the individual sites included in the HOVER trial. During the executive committee conference call, the local site will verify that the patient meets the

inclusion, and is free from exclusion criteria for the trial. The local site will present the patient's case for committee review. Any questions the executive committee may have regarding the case will be addressed during this call. If after the case presentation, 2/3 of the executive committee agree the patient is suitable for CAVI, the patient will be enrolled in the trial and an implantation date will be set. Documentation of approval for the trial of the patient by the executive committee will be added to the patient's chart. If all members of the executive committee are unable to convene on one conference call, the case will be presented individually to members of the committee in separate phone calls.

2.2.4 Use of Edwards-Sapien Transcatheter Valve

This trial represents the off-label use of an approved medical device. The on-label indications are as follows:

The Edwards SAPIEN 3 transcatheter heart valve (THV), model 9600TFX, and accessories are indicated for relief of aortic stenosis in patients with symptomatic heart disease due to severe native calcific aortic stenosis who are judged by a heart team, including a cardiac surgeon, to be appropriate for the transcatheter heart valve replacement therapy.

2.3 Statistical Analysis

A total of up to 15 patients will be enrolled. Due to the lack of preliminary data as well as exploratory nature of the study, no sample size and power analyses were performed. We expect to screen approximately 45 patients to enroll up to 15 eligible patients into this trial.

All clinically relevant baseline and follow-up data will be tabulated. Means (SDs), medians (ranges), and 95% confidence intervals will be reported for continuous variables and frequencies, percentages, and 95% confidence intervals for categorical variables. Specifically, each of the two primary endpoints (the procedural success at 30-days and the composite binary response variable at 6-months) will be summarized using both a point estimate and its exact confidence interval based on a binomial distribution. Other binary safety and efficacy secondary endpoints will be analyzed similarly. Continuous secondary endpoints (e.g., hemodynamics data) will be reported using descriptive summary statistics as well as a point estimate and its confidence interval based on a normal distribution assumption. The changes from baseline to each follow-up timepoint will additionally be evaluated using the McNemar matched pairs test for dichotomous variables and the t-test for continuous variables. In the presence of distributional non-normality, the Wilcoxon signed rank test will be used instead of the t-test. Data transformations such as log or square-root may also be considered. The analyses of NYHA functional classification will involve comparison of the baseline and post-operative (at each timepoint) functional class and determination of the percentages of patients improving, not changing, or worsening at each postoperative timepoint. The same principle will be applied to quality of life score (KCCQ) and 6-minute walk distance. Although this is an exploratory analysis, we anticipate 50% of patients will demonstrate improvement in one of the three pre-specified components of the primary efficacy outcome.

The time-to-event approach may be considered to analyze some of safety and efficacy endpoints (e.g., time to treatment failure, event-free survival, and overall survival) while taking censoring into account in data analyses. Such endpoints will be summarized using the Kaplan-Meier method. Confidence intervals for the medians and survival rates at different time points will be constructed, when appropriate. For a continuous endpoint measured repeatedly over time, a mixed-effects regression model may be employed to study its over-time trajectory or change patterns. All these results will be reported descriptively.

The intent-to-treat approach will be used for data analyses of this trial. That means all enrolled patients will be included in the interim and final data analyses regardless of their eligibility or subsequent events. Patients who are lost to follow-up or drop out of study prior to their scheduled follow-up evaluation time due to any reason will be treated as a treatment failure for response determination and censored for time-to-event type of endpoints at the time of their last follow-up if no relevant event has occurred by then. A secondary analysis that includes only all eligible patients may be conducted in addition to the primary analysis described above at the discretion of the trial PI and study biostatistician. However, such analysis may not serve as the basis for drawing conclusions concerning treatment safety or efficacy, and the reasons for excluding patients from the analysis should be clearly reported.

All enrolled patients will be evaluable for adverse events from the time of their protocol treatment. Adverse events will be tabulated by type and severity according to the NCI Common Terminology Criteria for Adverse Events (CTCAE) version 4.0.

During the entire study period, adverse events will be closely monitored by the trial PI and clinical trial coordinator of this study, working along with the study DSMB. In particular, formal stopping rules on the 6-month mortality are stipulated in this protocol (please refer to section 4.1 “Efforts to minimize procedure risks”). In addition, in the event that other adverse events (e.g., surgical complications) are thought to be excessive for the study patient population at any point of the trial, the patient accrual to the trial will be suspended immediately, pending a review of all adverse events data. A final decision will be made by the trial PI and DSMB as to whether the trial should be amended, terminated or continue accrual. Such decision should be filed with and pre-approved by the institutional IRB.

2.4 Study Endpoints:

The primary safety endpoint is procedural success at 30-days. Procedural success will include:

- Successful vascular access without unplanned major vascular complication as defined by VARC-2, delivery and retrieval of the transcatheter valve delivery system, correct position of both the vascular stent(s) and transcatheter valve in the IVC, a single valve placed within the IVC, and no need for additional surgery or re-intervention (including drainage of pericardial effusion) with the patient being alive at 30-days.

The primary efficacy endpoint will be improvement in one of three variables assessed from baseline to 6-months.

- Improvement of KCCQ score >15. This has been shown to correlate with improvement in quality of life with heart failure patients²².
- Improvement in 6-minute walk test (6MWT)>70 meters. This has been shown to provide prognostic information in patients with congestive heart failure after an intervention²³.
- Improvement of greater than 6% of peak Vo2 in cardiopulmonary exercise testing. In a heart failure population, this has been shown to help assess prognosis in patients who were instituted in an exercise program ²⁴.

Secondary endpoints will be evaluated at several timepoints and will be divided into safety and efficacy: The first in the acute setting which will be out to 30 days or hospital discharge whichever being longer; additional time points will be at midterm (6 months post-procedure), long term (1 year and annually up to 5-years post-procedurally.)

Secondary safety endpoints include:

- All stroke and TIA (VARC-2)
- Mortality (VARC-2)
- Myocardial infarction (VARC-2)
- Acute Kidney Injury (VARC-2)
- Major Vascular Complication (VARC-2)

Secondary efficacy endpoints include:

- Assessment of improvement of LE edema by the Villalta Score²⁵. A 3.1 point improvement in this scale was associated with improved quality of life²⁶.

Besides the above formal secondary endpoints, we will monitor for the following throughout the trial:

- Deep Vein/IVC thrombosis or pulmonary embolism
- Improvement in grades of tricuspid regurgitation as assessed by echocardiogram
- Changes in TAPSE by echocardiogram for RV function
- Pleural effusions
- Additional quality questionnaires to assess for changes in ascites (EORTC QLQ-C30²⁷ and ESAS-AM²⁸). A 10-point change in mean score in the QLQ-C30 has been shown to be a meaningful response (O'Connor R. Measuring Quality of Life in Health Churchill Livingstone: Philadelphia; 2004). A decrease of 1.25 points in the ESAS-AM has been shown to correlate with symptom improvement after paracentesis²⁸.

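### Late secondary safety endpoints default to crude all-enrolled proportions, with no rule for patients lost before the time point and censoring methods only optional

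*Combined protocol and SAP*

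**What the plan says.** Under section 2.3 each primary endpoint is "summarized using both a point estimate and its exact confidence interval based on a binomial distribution". The next sentence extends this: "Other binary safety and efficacy secondary endpoints will be analyzed similarly". The interval level is 95%, from the general statement that the plan reports "frequencies, percentages, and 95% confidence intervals for categorical variables".

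Section 2.4 lists the secondary safety endpoints as stroke/TIA, mortality, MI, AKI and major vascular complication, all by VARC-2. They are assessed acutely (to 30 days, or to discharge if later), at 6 months, and "long term (1 year and annually up to 5-years post-procedurally".

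On the analysis set, section 2.3 says "all enrolled patients will be included in the interim and final data analyses regardless of their eligibility or subsequent events". Section 5.7 adds that patients who discontinue early stay in the analysis and are not replaced.

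Section 2.3 has two rules for lost patients. They count as failures when response is determined, and they are censored at last follow-up in time-to-event endpoints. The second rule applies only if that type of analysis is chosen, and the plan says: "The time-to-event approach may be considered to analyze some of safety and efficacy endpoints". Its examples are time to treatment failure, event-free survival and overall survival.

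**The concern.** The only method to which the plan commits for a 5-year stroke or MI rate is a crude proportion in a set that keeps everyone enrolled. Neither rule for lost patients clearly reaches that proportion. A stroke is not a response, and the endpoint is not time-to-event unless someone later elects to analyse it that way. A patient lost at month 8 is therefore in the analysis set with no stated value for years 1 to 5.

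The analyst must choose a convention, possibly after seeing the data, and the choice can move the reported rate more than one or two real events would. Neither simple convention estimates the incidence when follow-up is incomplete, and a binomial interval on 15 treats follow-up as complete. Section 2.1 says durability beyond 6 months is poorly characterised and lists it among the questions the study should help clarify, so the late safety rates will be read.

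**Working it through.** The documents give no loss rate and no expected 5-year safety event rate, so there is no plan figure to reproduce. Two calculations show the size.

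**1. One dataset, three answers.** Input from section 2.3: "A total of up to 15 patients will be enrolled", so n = 15. Assumed: 3 observed events and 3 patients lost early without an event. The exact 95% limits for x events in n are the 2.5% quantile of Beta(x, n−x+1) and the 97.5% quantile of Beta(x+1, n−x).

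- Lost counted as event-free: 3/15 = 20% (4% to 48%).
- Lost counted as failures: (3+3)/15 = 6/15 = 40% (16% to 68%).
- Lost removed: 3/(15−3) = 3/12 = 25% (5% to 57%).

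If all three losses precede the first event or death, a censoring-based estimate equals the last of these point estimates.

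**2. Expected bias at 5 years.** Assumed constant, independent hazards:

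- Event: λ = −ln(0.70)/5 = 0.0713 per year, which gives 30% at 5 years when nobody dies of other causes.
- Loss: γ = −ln(0.90) = 0.1054 per year (10% annual loss).
- Death without the event: δ = 0; or −ln(1−0.331) = 0.4020, from the 33.1% one-year mortality cited in section 1.0; or −2·ln(0.70) = 0.7133, from the 30% six-month mortality assumed in section 4.1.3. Holding either mortality figure constant for 5 years is an assumption.

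Formulas, with S = λ+γ+δ:

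- True cumulative incidence = λ/(λ+δ) × [1 − exp(−5(λ+δ))]
- Lost = event-free: λ/S × [1 − exp(−5S)]
- Lost = failure: (λ+γ)/S × [1 − exp(−5S)]

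Worked for δ = 0.4020:

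- True: 0.0713/0.4733 × (1 − 0.0938) = 13.7%.
- Event-free: S = 0.5787, so 0.0713/0.5787 × (1 − 0.0554) = 11.6%.
- Failure: 0.1767/0.5787 × 0.9446 = 28.8%.

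| Death assumption | True | Lost = event-free | Gap (points) | Lost = failure | Gap (points) |
|---|---|---|---|---|---|
| None | 30.0% | 23.7% | −6.3 | 58.7% | +28.7 |
| 33.1% per year | 13.7% | 11.6% | −2.0 | 28.8% | +15.2 |
| 30% per 6 months | 8.9% | 7.9% | −1.0 | 19.6% | +10.7 |

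Gaps are taken before rounding.

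**Range over the assumed loss rate** (no deaths; 5%, 10%, 15% lost per year):

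- True 30%: event-free reading 26.7%, 23.7%, 21.0%; failure reading 45.8%, 58.7%, 68.9%.
- True 20%: event-free reading 17.7%, 15.7%, 13.9%; failure reading 38.1%, 52.8%, 64.5%.

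**The case against.** A reader might infer that lost patients count as event-free, so that the late rates always flatter the device and safety uses the opposite convention to efficacy. The documents do not support that. No section says a missing safety outcome is scored as no event, and staying in the analysis set does not by itself assign a value. The only imputation the plan states is failure, and applied to safety it pushes the rate up. The direction of bias is therefore open.

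Other points on the plan's side also have weight:

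- **Death shrinks the bias.** A patient who dies without a stroke belongs in the denominator of a cumulative incidence, so the crude proportion already handles what may be the main cause of incomplete follow-up. This stands, and the second and third table rows reflect it.
- **Some endpoints are barely touched.** AKI as defined in Appendix B requires the creatinine rise within 48 hours, and major vascular complications are largely access or procedure related. This stands.
- **Mortality has a safeguard.** Section 5.7 allows a death-registry search after withdrawal or loss. It is optional and recovers survival status only, so it protects mortality in part and stroke or MI not at all.
- **Interim truncation.** The formal looks in section 4.1.3 concern 6-month deaths, and no interim analysis of 1- to 5-year proportions is described. The point therefore rests on loss to follow-up, not on patients who have yet to reach a visit.
- **Low stakes.** This is an exploratory study in which "no sample size and power analyses were performed", and no stated decision turns on a 5-year secondary proportion. The intervals in the 15-patient example overlap heavily. This limits the importance of the point but does not supply the missing rule.
- **Kaplan-Meier is already there.** It is optional, and none of its examples is a named non-fatal safety endpoint.

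**Conclusion.** The point holds as a modest weakness of unspecified direction. The committed summary for late binary safety endpoints is a crude exact-binomial proportion with all enrolled patients included. The plan does not say how lost patients enter it, and the method that would handle them is optional. Either simple convention gives a worse estimate than a censoring-based one.

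In the 15-patient example the convention alone moves the rate from 20% to 40%. In expectation, with a 30% five-year event hazard and 10% annual loss, the event-free reading understates by about 6 points with no deaths and about 2 points with 33% annual mortality. The failure reading overstates by about 29 and 15 points. These sizes rest on assumed event and loss rates, constant hazards and loss unrelated to outcome.

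The point applies mainly to late stroke/TIA, MI and mortality, and hardly to AKI, access-related complications or anything within 30 days.

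**What to change.** In section 2.3, limit the sentence on other binary secondary endpoints and make the time-to-event approach mandatory for late safety. Suggested wording:

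*Secondary safety endpoints to 30 days will be summarised as proportions with exact 95% binomial intervals. At 6 months, 1 year and each year to 5 years, mortality will be estimated by Kaplan-Meier. Non-fatal safety events will be estimated by the cumulative incidence function with death as a competing event. Patients without the event will be censored at last contact. Estimates will be given with 95% confidence intervals and the number at risk at each time point. The failure rule for lost patients applies to efficacy response only.*

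No new data are needed: Table 1 schedules an event assessment at every follow-up visit to year 5, and the adverse event form records onset dates. The cost is a little more analysis work in standard software and, with at most 15 patients, wide late intervals that show openly how few patients remain under observation.
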